		EQ-5D VAS	
Single item. Range from 0 = "worst imaginable health state" to 100 = "best imaginable health state".
 
Note: higher value indicates better health state.
	Single item, missing if missing

Description and Derivation of Efficacy/Health Outcomes Measures and Endpoints

Measure	Description	Variable	Derivation/Comment	Definition of Missing
WPAI-Lupus	The Work Productivity and Activity Impairment – Lupus (WPAI:Lupus) is a patient-reported instrument developed to measure the impact on work productivity and regular activities attributable to SLE. It contains 6 items that measure: 1) employment status, 2) hours missed from work due to the specific health problem, 3) hours missed from work for other reasons, 4) hours actually worked, 5) degree health affected productivity while working, and 6) degree health. Scores are calculated as impairment percentages (Reilly et al. 1993), with higher scores indicating greater productivity impairment.	Employment Status	Yes/No	Missing if answer is missing
		Absenteeism Score (%)	$\frac{Q2}{(Q2 + Q4)} \times 100$	Missing if Q2 or Q4 are missing. Also missing if Employment Status is No.
		Presenteeism Score (%)	$\frac{Q5}{10} \times 100$	Missing if Q5 is missing. Also missing if Employment Status is No.
		Work productivity Loss Score (%)	$\left[\frac{Q2}{Q2 + Q4} + \left(1 - \frac{Q2}{Q2 + Q4} \right) \frac{Q5}{10} \right] \times 100$	Missing if Q2, Q4 or Q5 is missing. Also missing if Employment Status is No.
		Activity Impairment Score (%)	$\frac{Q6}{10} \times 100$	Missing if Q6 is missing. May still be present and non-missing if patient is unemployed.

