SLICC/ACR	Change from baseline in SLICC/ACR	ANCOVA with mLOCF	PP	Week 52 visit	Exploratory endpoint
SF-36 V2 acute	Change from baseline in MCS	MMRM	PP	Week 52 visit	Secondary endpoint
	Change from baseline in physical component score (PCS)	MMRM	PP	Week 52 visit	Secondary endpoint
	Change from baseline in domain scores SF-36 health survey version 2 acute	MMRM	PP	Week 52 visit	Secondary endpoint
EQ-5D-5L	Change from baseline in EQ-5D-5L US/UK population-based index scores and VAS	MMRM	PP	Week 52 visit	Secondary endpoint
	Proportion of patients with no problem in each EQ-5D-5L item score	Logistic Regression, NRI	PP	Week 52 visit	Secondary endpoint

Description of Efficacy/Health Outcomes Analyses

Measure	Variable	Analysis and Imputation Method	Datapoint Sets	TPI*	Analysis Type
WPAI-Lupus	Change from baseline in WPAI-Lupus ⁱ	MMRM	PP	Week 52 visit	Secondary endpoint

Abbreviations: AC = as collected; ACR = American College of Rheumatology Damage Index; ANCOVA = analysis of covariance; ANOVA = analysis of variance; BICLA = British Isles Lupus Assessment Group Based Composite Lupus Assessment; BILAG = British Isles Lupus Activity Group; CLASI = Cutaneous Lupus Erythematosus Disease Area and Severity Index; EQ-5D-5L = European Quality of Life-5 Dimensions-5 Level; FACIT = Functional Assessment of Chronic Illness Therapy; LLDAS = Lupus Low Disease Activity State; MCS = mental component score; MI = multiple imputation; mITT = modified intent-to-treat; mLOCF = modified last observation carried forward; MMRM = mixed model for repeated measures; NRI = non-responder imputation; NRS = Numeric Rating Scale; PCS = Physical Component Summary; PGA = Physician's Global Assessment; PP = per protocol; PPCV = per protocol COVID free; SFI = SLEDAI Flare Index; SLE = Systemic Lupus Erythematosus; SLEDAI-2K = Systemic Lupus Erythematosus Disease Activity Index 2000; SF-36 = Short Form 36; SRI-4 = SLE Responder Index; SLICC = Systemic Lupus International Collaborating Clinics; TPI = time point of interest; UK = United Kingdom; US = United States; VAS = visual analogue scale; WPAI-Lupus = Work Productivity and Activity Impairment Questionnaire: Lupus V2.0.

- ^a Population is a subset of mITT which includes patients with SLEDAI-2K score $\geq x$ at baseline (where x is 5, 6, 7, 8) for each SRI-x responder analysis.
- ^b Population is a subset of mITT which includes patients with SLEDAI-2K score >0 within the organ domain at baseline.

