- ^c Population is a subset of mITT which includes patients with at least one SLEDAI-2K item = 0 in the organ domain at baseline.
- ^d Population is a subset of mITT which includes patients with BILAG A or B in the organ domain at baseline.
- ^e Population is a subset of mITT which includes patients without BILAG A in the organ domain at baseline.
- ^f Population is a subset of mITT which includes patients with CLASI total activity score ≥ 10 at baseline.
- ^g Population is a subset of mITT which includes patients with > 7.5 mg/day prednisone at baseline. The logistic regression model covariates include treatment groups, baseline disease activity (total SLEDAI-2K <10 ; ≥ 10) and region (North America, Central/South America/Mexico, Europe, Asia and Rest of World).
- ^h Population is a subset of mITT which includes patients with > 0 mg/day prednisone at baseline.
- ⁱ For absenteeism score, presenteeism score, and work productivity loss score, population is a subset of mITT which includes patients who had employment status of Yes at baseline.
- * Assessments collected at multiple visits will be analyzed at each visit, in addition to the primary time point listed in the table.

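### The Work Productivity Loss score of WPAI-Lupus is set to missing when Q5 is blank, even where Q2 and Q4 alone fix it at 100%

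*SAP*

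**What the plan says.** SAP Section 6.10.1, Table JAIA.6.4, defines four WPAI-Lupus scores from six items. Q2 is hours missed because of lupus and Q3 is hours missed for other reasons. The next two items are "4) hours actually worked, 5) degree health affected productivity while working". Scores are impairment percentages, "with higher scores indicating greater productivity impairment".

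- Absenteeism is Q2/(Q2+Q4) x 100. Its missing rule is "Missing if Q2 or Q4 are missing. Also missing if Employment Status is No".
- Work Productivity Loss is [Q2/(Q2+Q4) + (1 - Q2/(Q2+Q4)) x Q5/10] x 100. Its missing rule is "Missing if Q2, Q4 or Q5 is missing. Also missing if Employment Status is No". There is no exception for a patient with no hours worked.

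Table JAIA.6.6 lists "Change from baseline in WPAI-Lupus" as a secondary endpoint, analysed by MMRM on the PP datapoint set at Week 52. Footnote i to that table says that for the three work scores the "population is a subset of mITT which includes patients who had employment status of Yes at baseline". Section 6.4 makes change from baseline the MMRM response and includes baseline value as a covariate. Section 6.4.2.2 states that the MMRM assumes missing at random.

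**The concern.** A score should be missing when its inputs leave it undetermined. Here one set of inputs determines the score without Q5, and the rule still requires Q5. The patient concerned is employed, worked no hours in the recall period and missed at least some hours because of lupus. Such a patient has no working time to rate, so a blank Q5 is a natural response to an item described as "5) degree health affected productivity while working".

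If Q5 is blank, the lost value is the maximum impairment score. The missingness then depends on the outcome itself, so the missing-at-random assumption is doubtful for those visits: the model would fill the gap from patients who did work. Average impairment would be understated, and if such records were more common in one arm, part of the treatment contrast on this sub-score would be lost.

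**Working it through.** **Inputs.** The formula and missing rule come from Table JAIA.6.4, the analysis from Table JAIA.6.6 and Section 6.4, and the baseline definition from Section 6.3. The SAP gives no WPAI means and no frequency of zero-hours records, so there is no figure of its own to reproduce.

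**Step 1: the formula at Q4 = 0, Q2 > 0.** Q2/(Q2+Q4) = Q2/Q2 = 1. The weight on Q5 is 1 - 1 = 0. The score is [1 + 0 x Q5/10] x 100 = 100%. Evaluating it at Q2 = 1, 8, 20, 40 and 60 hours, with every Q5 from 0 to 10, gives 100.0 each time.

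**Step 2: where Q5 does matter.** With Q2 = 20:

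| Q4 | Q5 = 0 | Q5 = 5 | Q5 = 10 |
|---|---|---|---|
| 0 | 100 | 100 | 100 |
| 1 | 95.2 | 97.6 | 100 |
| 8 | 71.4 | 85.7 | 100 |
| 20 | 50 | 75 | 100 |

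Requiring Q5 is right when Q4 > 0 and unnecessary when Q4 = 0 with Q2 > 0.

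**Step 3: what the rule removes.** With Q4 = 0, Q2 > 0 and Q5 blank, Absenteeism is 100%, Presenteeism is missing (reasonably, since nothing was rated) and Work Productivity Loss is missing although its value is known. At a postbaseline visit, that visit's value is lost and the MMRM keeps the patient's other visits. At baseline, Section 6.3 takes the last non-missing value before first dose; only if there is none does the patient have no change score on this sub-score at any visit.

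**Step 4: a neighbouring case.** With Q2 = Q4 = 0, both Absenteeism and Work Productivity Loss become 0/0. Neither missing rule covers this.

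**Step 5: scale, on assumed figures only.** Let s be the share of employed patients with Q4 = 0, Q2 > 0 and Q5 blank, and m the mean score among the rest. The full mean is (1 - s) x m + s x 100, so dropping these records lowers an arm's mean by s x (100 - m).

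- s = 1%, m = 40: 0.01 x 60 = 0.6 points.
- s = 5%, m = 40: 0.05 x 60 = 3.0 points.
- s = 10%, m = 25: 0.10 x 75 = 7.5 points.

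If m is the same in both arms, the hidden contrast is (s on placebo - s on baricitinib) x (100 - m).

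- 5% against 2%, m = 40: 0.03 x 60 = 1.8 points.
- 10% against 5%, m = 25: 0.05 x 75 = 3.75 points.
- 3% against 3%: 0 points.

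These are shifts in a mean at one visit. They are not the bias in the reported estimate, which is a change from baseline in a model that also uses baseline and the patient's other visits.

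**The case against.** The strongest objection is that the SAP never says Q5 is blank when Q4 = 0. The questionnaire and its data-entry rules are not shown, and if Q5 is answered the score is computed as 100% and nothing is lost. This stands, and it makes the harm conditional. It does not defend the rule, because an exception changes nothing where Q5 is answered.

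A reader might also infer four stronger things, none of which the SAP supports.

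- *That these patients drop out of the analysis.* Usually one visit of one sub-score is lost. Absenteeism and Activity Impairment remain for the same visit.
- *That a treatment which prevents lost weeks of work gets no credit.* Absenteeism needs only Q2 and Q4 and is analysed as its own score under the same endpoint, so full absence counts there.
- *That every such record is a week lost wholly to lupus.* Q3 records hours missed for other reasons. A record with Q2 = 2, Q3 = 38 and Q4 = 0 also scores 100% by the formula.
- *That the Absenteeism and Work Productivity Loss rows contradict each other.* They are different variables with different items, and one may be missing while the other is present. The fault lies within the Work Productivity Loss row, between its formula and its missing rule.

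The endpoint is also of limited weight: one of four WPAI scores, listed in Table JAIA.4.1 as not multiplicity-controlled, in patients employed at baseline.

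**Conclusion.** The rule is wrong as written, and the point is minor. That the score is 100% for any Q5 when Q4 = 0 and Q2 > 0 follows from the SAP's formula without assumption. That the rule then discards this value depends on Q5 being blank, which is plausible but not stated. Where it happens, missingness is tied to the worst outcome and missing at random is doubtful for those visits.

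The size is unknown. The illustrative 0.6 to 7.5 points on an arm's mean and 1.8 to 3.75 points of contrast rest wholly on assumed shares and means. The contrast also needs the shares to differ between arms; it is about zero if they are equal. No primary or major secondary inference is touched.

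The SAP already accepts the principle elsewhere in Table JAIA.6.4. For the absence of BILAG worsening, a domain that was A at baseline and is missing at the visit does not make the result missing, since it could not count as a new A or B. The WPAI row lacks the equivalent exception.

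**What to change.** Replace the Definition of Missing for Work Productivity Loss in Table JAIA.6.4 with: *If the patient is employed and Q4 = 0 with Q2 > 0, the score is 100% whether or not Q5 is answered. In all other cases the score is missing if any of Q2, Q4 and Q5 is missing, if Q2 + Q4 = 0 (formula undefined), or if the patient is not employed.* Add the Q2 + Q4 = 0 condition to the Absenteeism row as well, since it has the same denominator.

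This costs a sentence of SAP text and about one line of derivation code. It needs no new data and leaves every record with Q5 answered unchanged. A count by arm and visit of records with Q4 = 0, Q2 > 0 and Q5 blank would show whether the point matters in practice.

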To evaluate the effect of baricitinib 4-mg or 2-mg QD plus SoC compared to placebo plus SoC on SLE flares	
 Time to first mild/moderate flare over 52 weeks* Time to first flare (any severity) over 52 weeks Annualized mild/moderate flare rate Annualized severe flare rate Annualized flare rate (any severity)
To evaluate the effect of baricitinib 4-mg QD or 2-mg QD plus SoC compared to placebo plus SoC on mucocutaneous manifestations of SLE	
 Proportion of patients with CLASI total activity score ≥ 10 at baseline with $\geq 50\%$ reduction in CLASI total activity score at Week 52
To evaluate the effect of baricitinib 4-mg QD or 2-mg QD plus SoC compared to placebo plus SoC on musculoskeletal manifestations of SLE	
 Change from baseline in tender joint count at Week 52 Change from baseline in swollen joint count at Week 52
To evaluate the effect of baricitinib 4-mg QD or 2-mg QD plus SoC compared to placebo plus SoC on individual organ system disease activity	
 Proportion of patients with improvement in each SLEDAI-2K organ system versus baseline at Week 52 Proportion of patients with worsening in each SLEDAI-2K organ system versus baseline at Week 52
To evaluate the effect of baricitinib 4-mg QD or 2-mg QD plus SoC compared to placebo plus SoC on PROs	
 Change from baseline in Worst Fatigue NRS at Week 52 Change from baseline in Worst Joint Pain NRS at Week 52 Change from baseline in Joint Stiffness Duration at Week 52 Change from baseline in Joint Stiffness Severity NRS at Week 52 Change from baseline in Patient Global Impression of Severity at Week 52 Change from baseline in Patient Global Impression of Change at Week 52 Change from baseline in mental component score (MCS), physical component score (PCS), and domain scores in the Short-Form 36-item health survey version 2 (SF-36v2) acute at Week 52 Change from baseline in the EQ-5D-5L at Week 52 Change from baseline in the WPAI-Lupus at Week 52

Primary and Major Secondary Objectives and Endpoints

Objectives	Endpoints (Variables) ^a
To measure baricitinib PK exposure and assess the relationship between exposure and efficacy	
 Population pharmacokinetics of baricitinib in patients with SLE Proportions of patients achieving SRI-4 by exposure quartile

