6.4.2.1 Non-responder Imputation (NRI)

The non-responder imputation (NRI) method may be used when the estimand of interest uses the composite strategy (EMA 2020) for handling intercurrent events. In this strategy, patients will be considered non-responders for the NRI analysis if they do not meet the clinical response criteria or have missing clinical response data (based on each set of [Table JAIA.6.5](#)) at the analysis time point.

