PPCV	
For patients experiencing the ICEs of treatment discontinuation, study discontinuation, or prohibited medication use, observations after such ICEs will not be included in analysis (that is, will be considered as missing).
 
Data from patients experiencing treatment interruptions due to non-COVID related interruptions, such as, adverse events or abnormal labs, etc., will be included and used as is, per treatment regimen.
 
Data from patients experiencing off-drug interruptions 20 or more days due to COVID-19 will not be included (that is, will be considered as missing) until treatment resumption of 20 days or more.
	Addresses the clinically relevant question comparing the number of subjects able to both complete the study treatment and to achieve adequate response without further medication being required in a pandemic-free world. Targets treatment effect without potentially confounding influences of COVID-19.
PP	
For patients experiencing the ICEs of treatment discontinuation, study discontinuation, or prohibited medication use, observations after such ICEs will not be included in analyses (that is, will be considered as missing).
 
Data from patients experiencing treatment interruptions due to non-COVID related interruptions, such as, adverse events or abnormal labs, etc., will be included and used as is, per treatment regimen.
 
Data from patients experiencing off-drug interruptions due to COVID-19 will be included and used as collected.
	Addresses the clinically relevant question comparing the number of subjects able to both complete the study treatment and to achieve adequate response without further medication being required.
AC	
For patients experiencing the ICEs of treatment discontinuation, prohibited medication use, or COVID-19 off-drug assessments, observations after such ICEs will be included in analyses until the study discontinuation or the date of the Week 52 visit, whichever earlier.
 
The post-treatment follow-up period will not be included in the efficacy analysis.
	Addresses the clinically relevant question comparing the number of subjects able to achieve adequate response, regardless of adherence and treatment compliance, in resemblance to real-world expectations.

Abbreviation: AC = as collected; ICE = intercurrent events; PP = per protocol; PPCV = per protocol COVID free.

Table JAIA.6.6. Description of Efficacy/Health Outcomes Analyses

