Measure	Variable	Analysis and Imputation Method	Datapoint Sets	TPI*	Analysis Type
SRI-4	Proportion of patients achieving SRI-4 response	Logistic Regression, NRI + MI	PPCV	Week 24 visit, Week 52 visit	Primary endpoint (Week 52); major secondary (Week 24)
		Logistic Regression, NRI	PP	Week 24 visit, Week 52 visit	Supplemental
		Logistic Regression, NRI	AC	Week 24 visit, Week 52 visit	Supplemental
		Logistic Regression, NRI + MI	PPCV, Per Protocol population	Week 52 visit	Supplemental
		Logistic Regression, NRI + MI	PPCV	Week 52 visit	Sensitivity (Tipping point analysis)
SRI-x (where x is 5, 6, 7, 8)	Proportion of patients achieving SRI-x response ^a	Logistic Regression, NRI	PP	Week 52 visit	Secondary endpoint
SLEDAI-2K	Change from baseline in total SLEDAI-2K through Week 52 visit	MMRM	PP	Week 52 visit	Secondary endpoint
	Proportion of patients achieving reduction of ≥ 4 points from baseline	Logistic Regression, NRI + MI	PPCV	Week 52 visit	Secondary endpoint
		Logistic Regression, NRI	PP	Week 52 visit	Secondary endpoint
	Proportion of patients with no worsening in SLEDAI-2K compared with baseline	Logistic Regression, NRI + MI	PPCV	Week 52 visit	Supplemental
		Logistic Regression, NRI	PP	Week 52 visit	Supplemental
	Proportion of patients with improvement in each SLEDAI-2K individual organ systems versus baseline ^b	Logistic Regression, NRI	PP	Week 52 visit	Secondary endpoint
	Proportion of patients with worsening in each SLEDAI-2K individual organ systems versus baseline ^c	Logistic Regression, NRI	PP	Week 52 visit	Secondary endpoint

Description of Efficacy/Health Outcomes Analyses

Measure	Variable	Analysis and Imputation Method	Datapoint Sets	TPI*	Analysis Type
BILAG	Proportion of patients with no new BILAG A and no more than 1 new BILAG B disease activity score (compared with baseline)	Logistic Regression, NRI + MI	PPCV	Week 52 visit	Secondary endpoint
		Logistic Regression, NRI	PP	Week 52 visit	Secondary endpoint
	Proportion of patients with reduction of all baseline BILAG A to B/C/D and baseline BILAG B to C/D and no BILAG worsening in other organ systems, where worsening is defined as ≥ 1 new BILAG A or ≥ 2 new BILAG B	Logistic Regression, NRI+MI	PPCV	Week 52 visit	Supplemental
		Logistic Regression, NRI	PP	Week 52 visit	Supplemental
	Proportion of patients with improvement in each BILAG individual organ systems versus baseline ^d	Logistic Regression, NRI	PP	Week 52 visit	Exploratory endpoint

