	Proportion of patients with worsening in each BILAG individual organ systems versus baseline ^e	Logistic Regression, NRI	PP	Week 52 visit	Exploratory endpoint
PGA	Proportion of patients with no worsening in PGA (compared with baseline)	Logistic Regression, NRI+MI	PPCV	Week 52 visit	Secondary endpoint
		Logistic Regression, NRI	PP	Week 52 visit	Secondary endpoint
	Change from baseline in PGA score over time through Week 52 visit	MMRM	PP	Week 52 visit	Secondary endpoint
BICLA	Proportion of patients achieving BICLA response	Logistic Regression, NRI + MI	PPCV	Week 52 visit	Secondary endpoint
		Logistic Regression, NRI	PP	Week 52 visit	Secondary endpoint
		Logistic Regression, NRI	AC	Week 52 visit	Secondary endpoint

Description of Efficacy/Health Outcomes Analyses

Measure	Variable	Analysis and Imputation Method	Datapoint Sets	TPI*	Analysis Type
28 Tender/ Swollen Joint Count	Change from baseline in tender joint count	MMRM	PP	Week 52 visit	Secondary endpoint
	Change from baseline in swollen joint count	MMRM	PP	Week 52 visit	Secondary endpoint
CLASI Activity Score	The proportion of patients with \geq 50% reduction from baseline in total activity score ^f	Logistic Regression, NRI	PP	Week 52 visit	Secondary endpoint
SFI	Annualized severe flare rate	Negative binomial regression	PPCV	Through Week 52 visit	Secondary endpoint
		Negative binomial regression	PP		Supplemental
		Negative binomial regression	AC		Supplemental
	Annualized mild/moderate flare rate	Negative binomial regression	PP	Through Week 52 visit	Secondary endpoint
	Annualized flare rate (any severity)	Negative binomial regression	PP	Through Week 52 visit	Secondary endpoint
	Time to first severe flare	Cox regression	PPCV	Through Week 52 visit	Major secondary (Principal inference)
			PP		Supplemental
			AC		Supplemental
	Time to first flare (any severity)	Cox regression	PP	Through Week 52 visit	Secondary endpoint
LLDAS	Proportion of patients who achieve a LLDAS	Logistic Regression, NRI + MI	PPCV	Week 52 visit	Major secondary (Principal inference)
		Logistic Regression, NRI	PP		Supplemental
		Logistic Regression, NRI	AC		Supplemental

Description of Efficacy/Health Outcomes Analyses

Measure	Variable	Analysis and Imputation Method	Datapoint Sets	TPI*	Analysis Type

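### Applied as written, NRI counts dropouts and prohibited-medication users as not worsened in the organ-system worsening analysis, against the composite strategy and the PP estimand

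*SAP*

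**What the plan says.** Table JAIA.4.1 lists, among the other secondary endpoints outside multiplicity control, the "Proportion of patients with worsening in each SLEDAI-2K organ system versus baseline at Week 52". Table JAIA.6.6 assigns this variable, worded there as "Proportion of patients with worsening in each SLEDAI-2K individual organ systems versus baseline", logistic regression with NRI on the PP datapoint set at Week 52. An exploratory row, "Proportion of patients with worsening in each BILAG individual organ systems versus baseline", has the same method and datapoint set.

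Section 6.4.2.1 is the only definition of NRI: "patients will be considered non-responders for the NRI analysis if they do not meet the clinical response criteria or have missing clinical response data". It says that the method "may be used when the estimand of interest uses the composite strategy (EMA 2020) for handling intercurrent events".

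Table JAIA.6.5 says of treatment discontinuation, study discontinuation and prohibited medication in the PP set that "observations after such ICEs will not be included in analyses (that is, will be considered as missing". The question that this set is meant to answer concerns subjects "able to both complete the study treatment and to achieve adequate response without further medication being required".

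Table JAIA.6.4 defines the two worsening variables by the deterioration itself: a rise in the SLEDAI-2K domain score, or a move of a BILAG domain up to A or B.

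**The concern.** NRI is a conservative rule when the counted outcome is good, because a patient without data is then counted against the treatment. In these rows the counted outcome is bad. If the Section 6.4.2.1 wording is carried over unchanged, a patient who stops treatment or needs prohibited medication is scored as not worsened in every organ domain for which that patient is eligible. A plan that elsewhere treats these events as failure would here treat them as a good result.

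What is at stake is the reported worsening rates for both doses and placebo. When the arms differ in discontinuation or prohibited medication use, the treatment comparison is also affected.

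**Working it through.** **Text check.** Each place that could set the direction was read in turn.

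- Section 6.4.2.1 puts missing data in the same category as criterion not met.
- Table JAIA.6.4 makes deterioration the criterion. Its missing-data column says when a value is missing, not how it is then scored.
- Table JAIA.6.5 sets PP data after the three events to missing, so NRI alone decides the outcome for those patients.
- The paragraph before Table JAIA.6.5 says from which day a patient is an imputed non-responder, not which category that means for a worsening variable.
- Footnotes c and e of Table JAIA.6.6 define the eligible subset only.

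The literal result is therefore missing = not worsened. Compare two other rows in Table JAIA.6.6 with the same method and datapoint set. For the "Proportion of patients with improvement in each SLEDAI-2K individual organ systems versus baseline", a patient who discontinues is scored not improved, which is unfavourable. In the row for no worsening of total SLEDAI-2K, that patient is scored a failure. Only the worsening rows give the favourable score.

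**Arithmetic.** The SAP states no figure on this point, so there is none to reproduce. Let w be the worsening rate among patients with usable data and d the share with missing or post-event data. The SAP gives neither, so every value below is an assumption.

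- Literal coding (missing = not worsened): L = w(1 − d)
- Composite coding (missing = failure): C = w(1 − d) + d
- Within an arm: C − L = d
- Between arms: (C_act − C_pbo) − (L_act − L_pbo) = d_act − d_pbo, for any w

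| w placebo / active | d placebo / active | Literal, placebo / active | OR | Composite, placebo / active | OR |
|---|---|---|---|---|---|
| 10% / 10% | 30% / 20% | 7.0% / 8.0% | 1.16 | 37.0% / 28.0% | 0.66 |
| 15% / 10% | 30% / 20% | 10.5% / 8.0% | 0.74 | 40.5% / 28.0% | 0.57 |
| 10% / 20% | 30% / 20% | 7.0% / 16.0% | 2.53 | 37.0% / 36.0% | 0.96 |
| 10% / 10% | 25% / 25% | 7.5% / 7.5% | 1.00 | 32.5% / 32.5% | 1.00 |
| 15% / 10% | 25% / 25% | 11.25% / 7.5% | 0.64 | 36.25% / 32.5% | 0.85 |

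First row in full: 0.10 × 0.70 = 0.070 and 0.10 × 0.80 = 0.080, so the odds ratio is (0.080/0.920)/(0.070/0.930) = 1.155. Adding d gives 0.370 and 0.280, so the odds ratio is (0.280/0.720)/(0.370/0.630) = 0.662. The risk difference goes from +1.0 to −9.0 points, a shift of 20 − 30 = −10 points.

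The direction does not always reverse. With d of 30% and 20% and placebo w of 10%, it reverses only for active w between 0.070/0.80 = 8.75% and (0.370 − 0.20)/0.80 = 21.25%.

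With equal d the risk difference is the same under both codings. The odds ratio, which Section 6.4 uses for inference, still changes if w differs between arms (last row).

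**The case against.** The strongest reply is that the SAP applies one uniform rule: missing means the named criterion was not met. On that view a patient without data is counted neither as improved nor as worsened, and the two organ rows agree with each other. As a description of the rule this is correct. It does not rescue the worsening row, because Section 6.4.2.1 ties NRI to a composite strategy and the PP estimand counts stopping or needing more medication as failure. A uniform rule that scores those events favourably contradicts both.

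The comparison with the no-worsening rows is also imperfect. Those are whole-instrument variables, while the organ rows use domain-specific subsets and are not their complements. This is fair. The conflict rests mainly on the strategy and the estimand, and the paired organ-improvement row supports it.

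The objection that carries most weight concerns the remedy. A composite can be dominated by discontinuation: with w = 2% and d = 25% it reports 26.5%, of which 25 points are imputed. It can also hide real organ worsening. In the third row of the table, observed worsening on active is twice that on placebo, yet the composite reads 36% against 37%. The composite should therefore not stand alone.

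A reader might infer that the SAP mandates the favourable coding. It does not: what a responder means for a worsening variable is never defined, and a programmer who takes response as no worsening would code the opposite way without contradicting any sentence. A reader might also infer that the treatment effect will reverse. The documents give neither w nor d, so that is only a possibility under assumed values. For the BILAG row, Section 6.10.3.4 sends exploratory analyses to a separate SAP that is not shown, and that document may settle the direction.

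**Conclusion.** The point holds as a minor one. For the SLEDAI-2K organ-worsening endpoint, the imputation rule as written gives a result that conflicts with the SAP's own strategy and estimand, and no text corrects it. The BILAG row has the same form, subject to the separate exploratory SAP.

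The general size is an identity: each arm's rate differs between codings by its d, and the risk difference by the between-arm difference in d. Anything beyond that, including the change from an odds ratio of 1.16 to 0.66, depends on assumed rates. The endpoint is outside multiplicity control, and no primary or major secondary result depends on it.

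**What to change.** In the SLEDAI-2K row, and in the BILAG row unless the separate SAP already covers it, analyse no organ-domain worsening with NRI, so that missing or post-event data count as failure. Label the result a composite of organ worsening or treatment failure. Beside it, always report organ-worsening rates from the AC datapoint set, with the number of patients who have data, so that observed worsening stays visible.

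The cost is rewording and re-coding one or two rows and adding one descriptive summary for each. No new data are needed.
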